- 4.2.d. Pilot Trial: We used flyers, Internet ads and classroom presentations to recruit participants who met the same inclusion criteria used in the formative research above. Enrollment was conducted through the study website which provided a description of the research, informed consent with electronic signature, the baseline assessment, and randomization to either the TxM intervention or an attention control (CTL). Randomization was stratified on gender and heavy drinking (lower risk <3, high risk ≥3 HD episodes in the past 2 weeks). The TMAP intervention consisted of 6 weeks of two text messages sent in the evenings Thursday through Sunday. TMAP participants could also text Keywords to the program and receive automated reply texts that provided the number for local cab companies (keyword: Cab), online drink cost calculators (keyword: Cost), and additional tips on reducing drinking in specific situations (keywords: Party, Club). Those in the CTL group received general motivational, non-alcohol-related texts on the same schedule as the TMAP arm. Assessments conducted at baseline, end of intervention (week 6) and 12-week follow-up included a Timeline

Follow-back for alcohol use, 108,109 and measures of alcohol problems, protective behavioral strategies to limit drinking, 110 and self-efficacy in being able to limit/control drinking. 111

The first generation TMAP program used a hybrid web/SMS application implemented with the *Live Inspired* System Architecture using Java Enterprise Edition 5 (JEE) and Debian GNU/Linux. JEE is an industry-standard framework for development of server applications; among other services, JEE provides web request processing (with the Servlet API and Java Server Pages), data management (with the Java Persistence API), and distributed queuing (with the Java Message Service). Debian is an operating-system distributor, which packages, tests, distributes, and patches a wide-range of robust system and network tools.

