Changes in Alcohol Consumption and Consequences: Compared to controls, participants in the TMAP condition reported significantly fewer heavy drinking episodes at post-intervention ( $M_{\text{TMAP}} = 2.39$ , SD = 2.35 vs.  $M_{\text{CTRL}} = 4.07$ , SD = 4.29; Cohen's d = 0.48) and 12-week follow-up ( $M_{\text{TMAP}} = 2.06$ , SD = 2.10 vs.  $M_{\text{CTRL}} = 4.66$ , SD = 5.30; Cohen's d = 0.64). Participants also consumed less alcohol (drinks/week) at 12-weeks in the TMAP (M = 9.77, SD = 7.91) vs. control group (M = 10.83, SD = 8.42; Cohen's d = 0.13), and had fewer alcohol-related problems than controls at post-intervention ( $M_{\text{TMAP}} = 3.29$ , SD = 3.98 vs.  $M_{\text{CTRL}} = 4.81$ , SD = 4.83; Cohen's d = 0.34) and 12-week follow-up: ( $M_{\text{TMAP}} = 4.03$ , SD = 5.23 vs.  $M_{\text{CTRL}} = 5.21$ , SD = 5.85; Cohen's d = 0.21). While many of these changes are not statistically significant, this pilot study was not powered for significance. Its primary aims were to assess feasibility, acceptability and to obtain estimates of effect size. It is important to note that the magnitudes of the changes in the TMAP effect sizes are consistent with those reported in meta-analyses of alcohol interventions among traditional college students.  $^{32,76}$  Further, the frequency of heavy drinking was significantly reduced among participants in the TMAP condition (vs. control: d = 0.64, 95% CI = 0.13, 1.16). These findings are highly encouraging and indicate the need for a larger, rigorous trial to determine the robustness of this effect.

**Changes in Targeted Factors:** The TMAP group showed significant increases in self-efficacy in their ability to limit drinking (M = 58.4, SD = 25.6) at baseline to (M = 71.8, SD = 24.4) at post-intervention (p = 0.002). This increase was sustained through week 12. No changes in self-efficacy were observed in CTL participants. Use of protective strategies increased for TMAP participants from baseline (M = 1.6, SD = 0.7) to (M = 1.9, SD = 0.8) at post-intervention (p = 0.05; Cohen's d = 0.39), there was also a *decrease* in number of strategies used by CTL from baseline to week 12 (p = 0.05). Finally, there was a significant increase from baseline to post-intervention in TMAP participants' motivation to reduce drinking (p = 0.049). 

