Power Analysis: The proposed study is fully powered for our primary outcomes of heavy (episodic) drinking and alcohol-related problems. Results from our pilot study (section 4.2) indicated a d of 0.64 (95% CI = 0.13, 1.16) for heavy (episodic) drinking and 0.21 (95% CI = -0.32, 0.75) favoring the intervention at the 12week assessment (6-weeks post-intervention). When we assessed the presence (any) or absence (none) of alcohol-related problems at the 12-week assessment, we found a d of 0.66 (95% CI = 0.14, 1.18) favoring the intervention. Findings from a related pilot trial evaluating an extended internet-based intervention that included text messages (AHC; AlcoholHelpCenter.net) compared to CYD indicated a d of 0.41 (95% CI = 0.11, 0.72) on the Alcohol Use Disorders Identification Test for Consumption (AUDIT-C) at the 6-month follow-up. (The AUDIT-C is a brief screening measure used to assess hazardous drinking, including heavy drinking, and higher scores would indicate that the individual would likely be experiencing alcohol-related problems.) Therefore, we conservatively chose to power on a d of 0.41 across the 3- and 6-month assessments. This effect size is considered to be small to medium using Cohen's criteria. 136 It is important to note that our power analysis is based on our ability to detect differences in at-risk drinking between our two active conditions, CARES and CYD, across a 6-month follow-up. Given the aforementioned findings, and an alpha level of 0.05 and power of 0.80, a power analysis was conducted using GPower 3.0.137 This analysis revealed that 190 participants (95 per condition) would be required. Assuming an estimated attrition of 20% by the 6-month follow-up, approximately 238 participants (119 per condition) are needed. Thus, our proposed sample size of 250 (125 participants per group) will be sufficient to detect even small between-group effects on the hypothesized outcomes as well as controlling for covariates.

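### The power calculation at d = 0.41 does not support detection of even small effects, and does not show full power for the alcohol-problems count

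*Combined protocol and SAP*

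**What the plan says.** The Power Analysis (section 4.4.h) opens: "The proposed study is fully powered for our primary outcomes of heavy (episodic) drinking and alcohol-related problems". It cites three sources for the effect size:

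- The team's own pilot at 12 weeks: d = 0.64 for heavy drinking, followed by "0.21 (95% CI = -0.32, 0.75) favoring the intervention". That sentence does not name the outcome for the second figure, but section 4.2.d gives 0.21 as the 12-week effect on alcohol-related problems.
- The same pilot, any versus no problems at 12 weeks: d = 0.66.
- A related trial which, "compared to CYD indicated a d of 0.41 (95% CI = 0.11, 0.72", on the AUDIT-C at 6 months.

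It then states: "Therefore, we conservatively chose to power on a d of 0.41 across the 3- and 6-month assessments". On the size of that effect it says "This effect size is considered to be small to medium using" the usual criteria. It explains that the calculation concerns differences in at-risk drinking between the two arms, and that people with high AUDIT-C scores would probably be having alcohol problems. The stated result is 190 evaluable participants, 238 after attrition and 250 planned. The closing sentence is that this number "will be sufficient to detect even small between-group effects on the hypothesized outcomes as well as controlling for covariates".

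Elsewhere, section 4.2.d reports pilot effects on the problems count of 0.34 at the end of the intervention and 0.21 at 12 weeks. Section 4.4.h (Preliminary Analyses) says that the main analyses use counts, with any-versus-none variables as an optional addition.

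**The concern.** Two conclusions go further than the calculation beside them.

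1. A calculation at an effect labelled small to medium cannot show that small effects are detectable. The section's own label contradicts its last sentence.
2. Full power and conservatism are claimed for alcohol-related problems, but 0.41 comes from a consumption screen and is larger than both pilot effects on the problems count. The 0.66 that would support the claim is for a dichotomy, not for the count in the main analysis.

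At stake is how a null result on the problems count is read. Against this text, it would look like the result of a trial able to detect even small effects. The documents do not show that ability.

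**Working it through.** **Inputs from the documents.** d = 0.41, alpha 0.05, power 0.80, attrition 20%, 125 per arm enrolled (Power Analysis); 200 expected at 6 months, so 100 per arm (section 4.4.b). Sidedness is not stated.

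**The plan's figure.** For a two-sided two-sample t-test with noncentrality d·√(n/2) and 2n − 2 degrees of freedom, d = 0.41 needs n = 94.35, so 95 per arm and 190 in total. 190/0.80 = 237.5, so 238. Both match. A one-sided test gives about 75 per arm and does not match.

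**Pilot effects on the problems count**, from the means and SDs in section 4.2.d:

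- End of intervention: (4.81 − 3.29)/√((3.98² + 4.83²)/2) = 1.52/4.43 = 0.343.
- 12 weeks: (5.21 − 4.03)/√((5.23² + 5.85²)/2) = 1.18/5.55 = 0.213.

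Both match the stated 0.34 and 0.21.

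**Detectable effect by the same t-test at 80% power.** 0.398 with 100 per arm; 0.356 with all 125 per arm.

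**Allowing for the planned model.** Section 4.4.h (Aim 2.1) adjusts for baseline and uses the 3- and 6-month visits. The documents give no correlations, so these are assumptions: baseline correlation r_b from 0.3 to 0.7 and between-visit correlation r_v from 0.5 to 0.7. For a common effect on the mean of two visits, with roughly normal outcomes of equal variance, the effective standardised effect is

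d_eff = d / √((1 + r_v)/2 − r_b²)

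- Least favourable (r_b 0.3, r_v 0.7): √(0.85 − 0.09) = 0.872, so the detectable d is 0.398 × 0.872 = 0.347.
- Most favourable (r_b 0.7, r_v 0.5): √(0.75 − 0.49) = 0.510, so the detectable d is 0.398 × 0.510 = 0.203.

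**Power, two-sided 0.05:**

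| d | 100/arm, unadjusted | 125/arm, unadjusted | 100/arm, adjusted range |
|---|---|---|---|
| 0.20 (conventional small; the plan gives no number) | 29% | 35% | 36–79% |
| 0.21 (pilot problems, 12 weeks) | 32% | 38% | 40–83% |
| 0.34 (pilot problems, end of intervention) | 67% | 76% | 78% to over 99% |
| 0.41 (plan) | 82% | 90% | 91% to over 99% |

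On a grid of 15 correlation pairs (steps of 0.1), all 15 fall below 80% at d = 0.20, 14 at d = 0.21, one at d = 0.34 and none at d = 0.41.

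**The case against.** **The unadjusted figures are not for the test that will be run.** This stands, which is why the adjusted ranges are given. The likelihood-based model can also use 3-month data from people lost by 6 months. If all 125 per arm contribute at 3 months, power at d = 0.20 becomes 43–84%. It passes 80% at r_b 0.7 with r_v 0.5, but is at most 68% for r_b up to 0.6. A small-effects claim that needs near-best-case correlations has to state them, and the plan does not.

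**The plan says what it powered.** It does: at-risk drinking, with a reason for expecting AUDIT-C to track problems. That is a fair disclosure. But an association between high scores and problems does not show that the standardised effect on a problems count will be as large as the effect on AUDIT-C.

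**The pilot is weak evidence against 0.41.** This also stands. A reader might infer from 0.34 and 0.21 that the trial is underpowered for problems and needs more participants. The documents do not support that. The pilot interval, −0.32 to 0.75, includes 0.41 and rests on 57 people at 12 weeks. The pilot tested a 6-week text-only programme, and "Those in the CTL group received general motivational, non-alcohol-related texts on the same schedule as the TMAP arm". The trial has a longer app-based programme and an active control, so the effect could move either way. The 0.41 comes from a comparison with this trial's own control at 6 months. Because the model pools two visits, the lower pilot value alone is also too harsh a benchmark. The two average about (0.34 + 0.21)/2 ≈ 0.28, where adjusted power is 62–97%.

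**Problems may not be primary.** Section 4.4.e attaches the singular term primary outcome to heavy drinking days. But the Power Analysis names both outcomes as primary, and H1 in Aim 2.1 covers both.

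**Conclusion.** The concern holds as two unsupported conclusions drawn from correct arithmetic. It is a modest fault of wording and reporting, not of sample size.

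- The small-effects claim is not supported. The detectable effect with 200 completers is d = 0.40 by the plan's method, and about 0.20–0.35 under the planned model with the assumed correlations.
- Full power and conservatism are not shown for the problems count. The 0.41 is an AUDIT-C point estimate with its own interval of 0.11 to 0.72. Conservatism is fair for heavy drinking (pilot 0.48 and 0.64) and for any versus no problems (0.66).

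The documents show neither adequate nor inadequate power for the problems count. At an effect near 0.34 the planned model would do well almost throughout the assumed range; the gap is mainly at 0.20–0.21. The adjusted figures rest on assumed correlations and on treating counts, possibly over-dispersed or zero-inflated, as roughly normal with equal variances. They indicate a range only.

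**What to change.** In the Power Analysis of section 4.4.h:

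1. Delete the claim about even small effects and put in its place: *With 200 completers, power is 82% for d = 0.41 (80% for d = 0.40) per two-sided 0.05 test, before any gain from baseline adjustment and repeated measures.*
2. Limit the full-power claim to heavy drinking. Limit the description of 0.41 as conservative to heavy drinking and to any versus no problems.
3. For the problems count, either justify 0.41 or report power at d = 0.21 and d = 0.34 under the planned model, with its correlations stated. The pilot measured problems at baseline, week 6 and week 12, so it can supply correlations. They are proxies only, because the trial's visits are at 3 and 6 months and section 4.2.d does not name the pilot's problems measure.

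The cost is a few sentences and a short power table. The sample size, analysis and conduct do not change. The downside for the sponsor is that the stated power for the problems count becomes less favourable.

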#### 5. PROTECTION OF HUMAN SUBJECTS

# 5.1. Risks to Human Subjects:

**5.1.a.** Human Subjects Involvement and Characteristics: Subjects will include male and female students (N=40 for Phase I and N=250 for Phase II) attending community college who are age 18-29 and who report at least two heavy drinking episodes in the past two weeks (5 or more drinks for men, 4 or more for women). Subjects will be recruited through flyers, classroom presentations and campus internet advertisements targeted to the student population at the Community College of Rhode Island (CCRI) and Bristol Community College (BCC: see letters of support). Based on our prior experience recruiting participants for college drinking interventions and interview studies,  our very successful recruitment in the pilot trial, and the student pool at both CCRI and BCC, we anticipate that we will be able to recruit all participants needed for this study within the proposed timeline. Our project staff will solicit feedback from professionals who work with community college students and students themselves. This advisory board will be chaired by [name] (Consultant) who is a member of the faculty at CCRI. The advisory board will consist of at least 2 persons in each category: Administrators, teachers, students and student services workers. These advisory board members will meet twice annually and review our program as content experts and are not considered research subjects.

5.1.b. Population and Setting: This study will be conducted with students at two college systems serving the region: Bristol Community College (BCC) located in Fall River, MA (with four locations across southeastern Massachusetts), and the Community College of Rhode Island (CCRI), which has six locations throughout RI. Student populations at both colleges are comparable, with approximately 11,000 students enrolled annually, about 35-40% of whom are heavy drinkers. 9,11 Approximately 80% of students are between ages 18 and 29 (the age group of interest in this study), and of these, 48% are ages 18-20. Thus, we are confident that there will be sufficient numbers of eligible students who will be available to enroll in the study. We were able to over-recruit for our pilot trial (section 4.2) using the same eligibility criteria as we will use for both Phase I and II of the proposed STTR project.

Approximately 56% of the students at BCC and CCRI are women. The current ethnic and racial distribution of the student population at CCRI and BCC are similar. Approximately 12% are Black/African American, 3% Asian, 1% Native American, 1% Native Hawaiian or Other Pacific Islander, 75% White and 8% more than one race. Approximately 20% of students are Hispanic. However, nationally enrollment at community colleges and similar 2-year institutions is approximately 50% ethnic and/or racial minority. Therefore we will over-recruit to ensure that approximately 50% of our study participants will be ethnic and/or racial minorities. This is similar to the overall population in the greater Providence, RI area. Both colleges maintain a small student services office, but health services are not available on campus.

5.1.c. Recruitment Procedures: Participants will be recruited through flyers, classroom presentations and emails to students meeting age criteria at CCRI and BCC. Ads will provide a brief description of the study, a study website and a contact phone number, allowing individuals to access information about the study by phone or internet. Recruitment materials will emphasize that community college professors and administrators will not have access to information about participants. The website will provide a description of the study and an option to continue to online screening questions. For those calling by phone, project research staff will briefly explain the study and answer any questions, then will direct interested callers to the website to complete the screening. At the end of the screening survey, respondents will be asked to provide their community college email address. Our web-based survey system will be programmed to determine the eligibility of respondents, check the provided email address against prior respondents, and send the eligibility information only to valid email addresses (e.g., ccri.edu or bcc.edu) that have not previously been used. These procedures will ensure that respondents will not be able to complete the screener more than once. Email addresses will be stored in a separate data table from screening responses (linked by a unique ID), allowing us to maintain confidentiality.

Those not eligible will see a message informing them that they are ineligible because they do not meet the criteria for the study (the specific criteria will not be provided to avoid individuals sharing this information with others). Ineligible individuals will also be provided with a list of local and online resources for alcohol education and treatment.

Eligible individuals will be sent a link to their college email address. By clicking the link embedded in that email, the individuals will access the next set of web pages that explain the study in detail and present the IRB approved consent form for electronic signature. As part of the consenting process individuals will answer a series of true/false questions to ensure they understand the fundamentals of enrolling in a research study (e.g., this is a research study, your information is confidential, you may withdraw at any time, etc.). A phone number is also provided on the website so that individuals can call our study staff with any questions regarding the study or the consent.

After providing an electronic signature for consent, participants will complete a contact information form (name, address, email, phone, locator contact). Contact information is stored in a secure database separate from survey data to protect participant privacy and the confidentiality of their data. The participant will then have a 24-hour window in which to complete the baseline survey. When the survey is complete, the tracking system (used for assessment reminders and compensation payments) will be automatically updated. Eligible participants who do not complete enrollment or who enroll but do not complete the baseline survey will be contacted by telephone.

The online enrollment system will be programmed to follow the randomization scheme (stratified by age over/under 21, gender, and heavy drinking frequency) developed by [name] (Co-I). At the completion of the baseline survey participants will be informed about their assignment and given instructions. This information will also be sent via email. Participants assigned to the control condition will be routed to www.checkyourdrinking.net and will be instructed to complete the Check Your Drinking assessment within 7 days. Participants randomized to receive CARES will receive instructions on how to download the CARES app by first sending a text message to the dedicated phone number at *Live Inspired*. This phone number will reply with a link that will open in the appropriate App Store to download the Live Inspired application. In addition, the system will then send a message containing a code number that the participant must enter into the Live Inspired application (similar to verification codes used by online vendors) to connect them to the study.

CARES will push text messages twice daily on Thursday, Friday, Saturday and Sunday weekly for 12 weeks, following the schedule recommended by our focus groups of community college students and tested in our pilot study. Message content focuses on alcohol education, motivation, building self-efficacy, caring messages, and strategies for risk reduction (section 4.4.c). Information provided about CARES will include key functions participants can use with the system as desired (e.g., clicking a button labeled "CAB" will return a list of contact phone numbers for local cab companies and a link to Uber). Following each content related text message sent by CARES, the system will send a follow up message asking the participant to rate the message they received on a scale of 1-10 to indicate how well they liked that specific message.

All participants regardless of randomization assignment will receive information about the assessment schedule and associated compensation. Assessments will be conducted at baseline/enrollment, weekly through text messages, and at 3- and 6-month follow-up.

Data from all surveys will be linked with the individual's study ID. For those receiving CARES, use of the app will also be linked to the individual's study ID. We used this online recruitment method very successfully in our previous studies. All direct human subjects involvement for this study and analysis of data will be performed at The Miriam Hospital site.

5.1.d. Inclusion/Exclusion Criteria: (1) age 18-29; (2) current CCS; (3) report ≥ two heavy drinking episodes (HDEs) in the past two weeks (This pattern is called Frequent Binge Drinking and should net a group of regular heavy drinkers); (an HDE is defined as 5 [4] or more drinks in one sitting for men [women]);

-  (4) has a smartphone and uses apps and text messaging; and (5) speaks and reads English comfortably. Due to safety concerns, we will exclude participants who (1) receive a score >14 on the Alcohol Dependence Scale (indicating substantial dependence),  or (2) report prior or current alcohol treatment (these individuals will be provided information about local treatment options).
- **5.2. Sources of Research and Clinical Material:** The research and clinical material for the proposed study will consist of questionnaires collected as electronic survey instruments concerning the following areas: sociodemographic characteristics (age, gender, ethnicity, household income, employment, parental status [that is, being the parent of minor children and whether those children live with the participant]); drinking habits and substance use history (current levels of drinking and/or substance use, any prior treatment history); a series of assessments relevant to examining posited mediators and moderators of intervention efficacy (e.g., motivation, self-efficacy); and items concerning current drinking behaviors. Weekly text messages will be sent to all participants regardless of randomization assignment to assess current drinking (see section 4.4.e for detailed descriptions of the assessment instruments and schedule of assessments).
- 5.3. Potential Risks: The risks in this study are considered minimal. The primary risk to participants in all phases of this study is loss of confidentiality of information shared via the questionnaires or materials provided to researchers. Participants may experience some emotional discomfort responding to questions about their alcohol use and beliefs but we do not consider this potential risk to be either common or serious.

